
mental health intervention to suggest conducting different studies in the recent systematic review by Akgün et al. (2019).

Accordingly, the primary aim of the current study is to test the efficacy of the online training program on mental health (DASS-21 and its subscales) regarding autistic traits. The secondary aim of the current study is to test the efficacy of the online training program on executive functions (working memory, inhibitory control, and cognitive flexibility), and social cognitive skills (cognitive empathy and affective empathy).

The following two hypotheses were addressed in the current study:

- 1. Online training on executive functions and social cognitive skills will promote mental health by reducing DASS-21 and its subscales scores in the current sample.**
- 2. Online training on executive functions and social cognitive skills will promote executive functions (working memory, inhibitory control, and cognitive flexibility) and social cognitive skills (cognitive empathy and affective empathy) in the current sample.**

[figure not shown]
Methods Study Design

The present study adopted a multifactorial design including pretest and posttest conditions to test the efficacy of combined EFs and social cognition online training via computers, tablets, or smartphones for mental health symptoms (depression, anxiety, and stress) in the experimental and control groups. Multifactorial design also called mixed design refers to including both within- participant design (testing the same participants over time) and between-participant design (comparing different groups, Breakwell et al., 2012). The independent variable for this study is online training while the dependent variables are mental health scores (depression, anxiety, and stress symptoms), executive functions (cognitive flexibility, inhibition, and working memory), and social cognition (cognitive empathy and affective empathy). According to our previous findings

(Chapter 4), autistic traits are included in this study as covariates, which are defined by characteristics that might affect the study's outcome (Cambridge University Press, n.d.).

Participants

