A power analysis (G*Power) was conducted to determine the number of participants needed to achieve this goal. For repeated measures analyses, 44 participants are required in order to reach a medium effect size of .25 with an adequate power of .80 at $\alpha = .05$ (Faul et al., 2009) to determine interaction effects of between and within participants' factors. Convenience sampling via advertisement through social media, mail groups, and on campuses was used to collect participants. Initially, 178 adult participants were recruited for this study to reach adequate power for multivariate analysis. Participants randomly and equally were assigned to the experimental group (89 participants) and control group (89 participants) to see whether the combined training program was effective for the general population. 33 participants for the experimental group and 48 participants for the control group completed the posttest. However, after checking outliers and normality analysis, 31 participants for the experimental group (28 female, 3 male), and 34 participants for the control group (29 female, 5 male) were included in the further analyses. Please see the figure 6.1. the flow of participants through each stage of the study. The details of the participants were presented the Table 6.1. Demographic Characteristics. To reduce drop-out, incentives such as drawing for money/prizes were used. Inclusion criteria for adult participants are being aged 18 or above, being able to use computers, smartphones, or tablets, being native Turkish citizens, having no record of any psychiatric disorders, and having no record of any physical and neurological conditions that prevent to use of technological devices. Participants who are under the age of 18 and have any record of psychiatric and physical conditions that prevent to use of technological devices were excluded from the study.

Materials

Self-Report Questionnaires

Figure 1. The Flow of Participants

Demographic Information Form

Basic information such as age, gender, education level (i.e., undergraduate, postgraduate), and income was obtained from the participants, and it was developed by the researcher.

Autism Quotient (AQ) for Adults Turkish Version (Baron-Cohen et al., 2006; Baron-Cohen et al., 2001a; Köse et al., 2010)

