completion of the research studies, the control group (on the waiting list) is scheduled to access the online training program in accordance with ethical guidelines.

Data Analysis

The data from the current study was analyzed using the SPSS 25.0 package. Initial analyses were performed to determine if the data showed a normal distribution. Before conducting parametric tests, the Shapiro-Wilk test, box plots, and skewness and kurtosis scores were used to check for normal distribution. The self-report questionnaires' data was found to be normally distributed according to the Shapiro-Wilk test ($p > .05$). As for the performance tasks, the skewness and kurtosis of the data fell within an acceptable range for applying parametric tests, as specified by Hair and colleagues (2010). Covariate analyses were conducted to account for the effects of autistic traits in the intervention model. Before including covariates in the analyses, correlation analyses and tests for homogeneity of regression slopes were performed according to the assumptions of covariance (Field, 2013). The results showed that only communication and attention-switching had significant correlations with dependent variables ($p < .05$) and met the assumptions for being used as covariates for mental health symptoms (Field, 2013). Regarding EFs and social cognitive skills, communication, attention to detail and imagination entered as covariates in the model ($p < .05$); however, only communication met the assumptions for homogeneity of regression slopes for EFs and social cognitive skills (Field, 2013). All correlation tables for these assumptions were presented in Appendix C, D, and E. Moreover, t-test analysis was carried out to see whether the pretests of dependent variables and AQ and its subscales for experimental and control groups

differ. Due to more than 8 variables; a conservative p -value was set ($p = .01$). The results showed no significant differences in all pretest scores and AQ (all $ps > .01$).

In the experimental study, 2 x 2 mixed design repeated measure ANOVAs were conducted to examine the group (experimental and control group) and the effects of time (pretest and posttest) on mental health (DASS-21 and its subscales), as well as executive functions (working memory, inhibitory control, and cognitive flexibility), and social cognitive skills (cognitive empathy and affective empathy). In terms of performance tasks, to ensure standardized measurement, errors

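### Each group-by-time test is a change-score test that never adjusts for the pretest; it is not in error, but a post hoc ANCOVA would usually be more precise, and each ANOVA's autistic-trait covariates need listing

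*Combined protocol and SAP*

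**What the plan says.** The Data Analysis section states that "2 x 2 mixed design repeated measure ANOVAs were conducted to" examine group (experimental, control) and time (pretest, posttest) on DASS-21 and its subscales, the executive-function tasks and the two empathy measures. The Participants section bases the sample size on a repeated-measures analysis "to determine interaction effects of between and within" participants' factors, so group-by-time is the effect of interest. The Procedure section places the pretest before assignment.

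The pretest is used in two ways: as one level of the time factor, and in between-group t-tests at p = .01, of which the text reports "The results showed no significant differences in all pretest scores and AQ".

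The only covariates named are autistic-trait (AQ) scores. Study Design says that "autistic traits are included in this study as covariates". Data Analysis says that covariate analyses were done in the intervention model. For mental health it reports that communication and attention-switching "met the assumptions for being used as covariates for mental health symptoms". For executive functions and social cognition it says "communication, attention to detail and imagination entered as covariates in the model", and then that "only communication met the assumptions for homogeneity of regression slopes for EFs and social cognitive skills". The sentence that defines the ANOVAs names no covariate.

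**The concern.** A change-score test fixes the slope of posttest on pretest at 1. When the true slope is below 1, which is the usual case, fixing it carries pretest noise into the estimated effect. Estimating the slope by ANCOVA removes that noise for one degree of freedom. Only 65 of 178 randomised participants are analysed, so precision is scarce and the pretest data are already in hand. The balance check does not do this job, because a non-significant pretest difference adjusts nothing.

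A second, smaller matter is that a reader cannot tell exactly which model produced each result. The text does not say which AQ subscales each ANOVA carried, whether the executive-function and social-cognition model kept three subscales or only communication, or whether unadjusted versions were also run. Nor would AQ adjustment stand in for the pretest: in a repeated-measures ANOVA a between-person covariate affects group-by-time only through its relation with change.

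**Working it through.** **The plan's own figure.** Participants gives N = 44 for f = .25, power .80 and alpha .05, without the pre-post correlation that the calculation needs. The usual within-between interaction formula (noncentrality f² × N × 2/(1 − rho), df 1 and N − 2) gives N = 66 at rho = 0, 34 at .5, and 28 to 24 at .61 to .68. It gives 44 only for rho of about .34 to .36. So 44 is attainable but cannot be confirmed from the stated inputs. Nothing below depends on it.

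**Inputs.** Analysed n = 31 and 34 (Participants). Test-retest r = .68 depression, .66 anxiety, .61 stress (DASS-21 description, from the Turkish adaptation study, interval not given). Assumptions: these r values approximate the six-week correlation; SD = 1 at both times unless stated.

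**Equivalence.** On a simulated data set with 31 and 34 per arm, the group-by-time F and the squared change-score t were both 4.5145 on 63 df.

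**Variance, equal SDs.** Each expression is multiplied by (1/31 + 1/34) = .0617.

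- Change score: 2(1 − r)
- ANCOVA: (1 − r²) × 62/61, where the last factor is the cost of estimating the slope
- Ratio: (1 + r)/2 × 62/61

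| r | Ratio | Reduction | 95% CI half-width, change | ANCOVA | Narrower by |
|---|---|---|---|---|---|
| .61 | .818 | 18.2% | .438 SD | .397 SD | 9.5% |
| .66 | .844 | 15.6% | .409 SD | .376 SD | 8.1% |
| .68 | .854 | 14.6% | .397 SD | .367 SD | 7.6% |

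Simulation (600,000 replicates per r) gave reductions of 18.1%, 15.6% and 14.4%. In sample-size terms, 65 would behave like 65/.854 = 76 to 65/.818 = 79.

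**Unequal SDs.** With k = post/pre SD, the ratio is k²(1 − r²)/(1 + k² − 2rk) × 62/61.

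| k | r = .61 | r = .66 | r = .68 |
|---|---|---|---|
| 0.8 | .615 | .629 | .634 |
| 1.25 | .961 | .982 | .990 |
| 1.4 | .999 | 1.011 | 1.014 |
| 1.5 | 1.011 | 1.016 | 1.016 |

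**Other outcomes.** No r is given for DASS-21 total or any performance task. At an assumed r of .3 to .8 with equal SDs, the ratio is .661 to .915, a reduction of 34% to 9%.

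**With one AQ subscale in both models.** Let a and b be its correlations with pretest and posttest (assumed, .1 to .4).

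- Change score + AQ: 2(1 − r) − (b − a)²
- ANCOVA + AQ: 1 − (r² + b² − 2rab)/(1 − a²)
- Ratio of the second to the first, times 61/60

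At r = .68, a = .4, b = .1: .5024/.55 × 61/60 = .929. At r = .61, a = .1, b = .4: .5118/.69 × 61/60 = .754. The reduction over this range is therefore about 7% to 25%.

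**What the balance check allows.** The SE of a pretest gap is √.0617 = .248 SD. The largest gap with p > .01 is t(.995, 63) × .248 = .66 SD. A gap of that size separates the two estimates by (1 − r) × .66 = .21 to .26 SD. This is part of the variance difference already counted.

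**Analysed set.** "33 participants for the experimental group and 48 participants for the control group completed the posttest", out of 89 each: 33/89 = 37% and 48/89 = 54%. After outlier and normality checks 31 and 34 remain, so exclusions were 2/33 = 6% and 14/48 = 29%.

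**The case against.** The strongest reply is that this is an efficiency choice, and a modest one. The group-by-time test is a legitimate analysis. At the planned f = .25, which with two arms and two times is a 1.0 SD difference in change, both analyses have power above .99 at 31 and 34 under these r values. That stands: the gain is precision, and no error in the test is shown.

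The 15-18% also rests on borrowed reliabilities and on equal SDs. At a post/pre SD ratio of 1.4 or more the gain vanishes. That stands too, and the figure should not be carried over to DASS-21 total or the performance tasks.

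A reader might infer from the bare ANOVA sentence that the plan is silent on AQ adjustment. It is not: Study Design and Data Analysis both say that autistic traits were covariates. What is unstated is the covariate list of each ANOVA and whether unadjusted versions were run. Because the slopes check is described as coming before inclusion, the likelier reading is that only communication was kept for executive functions and social cognition, but the text also says that three subscales entered.

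Finally, a second estimate chosen after the data are analysed adds room to select. That is a fair worry. It is met by giving the ANCOVA one fixed role, reporting it for every outcome, and leaving no optional covariate.

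**Conclusion.** The point holds as one of precision. The pretest is never a covariate, and ANCOVA would usually give a tighter estimate: about 15-18% lower variance for the DASS-21 subscales, if r is .61 to .68 and the pre and post SDs are equal. At the same r the range runs from 37-38% at an SD ratio of 0.8 to about nil at 1.4 or more. AQ adjustment does not replace the pretest; with one subscale in both models the reduction is still about 7-25%, on assumed correlations. The two-subscale case named for mental health was not computed.

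Two stronger readings are not supported. One is that the ANOVAs are invalid because they omit the pretest; they are not. The other is that ANCOVA would make the comparison sound. Completion and later exclusions differed by arm, so randomisation protects neither estimate in the 65 analysed, and a pretest gap there need not be chance. ANCOVA does not repair this. The two analyses may also target different effects in that set, which is a reason to show both.

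**What to change.** - For every outcome, fit posttest on group and that outcome's own pretest, with the same AQ covariates as the reported ANOVA or with none, and say which.
- Report the adjusted difference with a 95% CI, labelled a post hoc sensitivity analysis, beside the original ANOVA, for all outcomes whatever the result.
- List the covariates in each reported ANOVA. Say whether the executive-function and social-cognition models kept three subscales or only communication, and whether unadjusted versions were run. Reconcile Study Design and Data Analysis accordingly.
- State that neither estimate is protected by randomisation in the 65 analysed, giving completion (33/89 and 48/89) and later exclusions (2/33 and 14/48), and that ANCOVA does not repair this.

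The cost is one degree of freedom per covariate, a re-run on data already collected, and post hoc status for the added model.
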